To create the protocol summary form, first indicate if this research will include any of the following procedures

- ✓ Psychiatric Assessment
- ✓ Collection of Biological Specimens
- ✓ Medication Trial

Population

Indicate which of the following populations will be included in this research

- ✓ Medically and Psychiatrically Healthy Subjects
- ✓ Adults
- ✓ Adults over 50
- ✓ Individuals with HIV/AIDS

Research Support/Funding

Will an existing internal account be used to support the project?

Yes

Describe internal account

Gift account at RFMH

Is the project externally funded or is external funding planned?

No

Study Location

Indicate if the research is/will be conducted at any of the following

NYSPI

This protocol describes research conducted by the PI at other facilities/locations

No

Lay Summary of Proposed Research

Lay Summary of Proposed Research

We will enroll 30 opioid-dependent participants into an open-label pilot outpatient study of methods to facilitate induction and stabilization onto XR-NTX. There will be three different methods of XR-NTX induction.

Procedure 1: 5-day induction with 1 day of BUP (8 mg) followed by washout day and 3 days of oral NTX titration. Participants will receive XR-NTX on day five together with BUP 4 mg, and will continue receiving BUP for 4 weeks until they receive 2nd XR-NTX dose.

Procedure 2: 10-day induction with BUP 8 mg administered on Day 1 and 4 mg administered starting day 2 and increasing daily doses of NTX beginning on day 2 (0.25, 0.5, 1, 2, 3, 6, 12, 25). On day 10 participants will receive XR-NTX dose, and another one 4 weeks later. No BUP will be given beyond day 10.

Procedure 3: 10-day induction with BUP 8 mg administered on day 1 and 4 mg administered starting day 2 and increasing doses of NTX beginning on day 2 (0.25, 0.5, 1, 2, 3, 6, 12, 25). On day 10 participants will receive XR-NTX dose, and another one 4 weeks later. BUP 4 mg/d will continue for 4 weeks until the 2nd XR-NTX dose.

All participants will receive weekly therapy with a study psychiatrist. All participants will receive open-label medication.

We will first enroll all participants into Procedure 1 followed by Procedure 2 and Procedure 3.

The primary outcome of this study will be percentage of patients who receive the second injection of XR-NTX, Secondary outcomes will include measure of opioid withdrawal and illicit opioid use.

Background, Significance and Rationale

Background, Significance and Rationale

Agonist-based strategies (methadone and buprenorphine) have dominated the treatment of opioid dependence in the US for the last 40 years. However, agonists are not effective for all patients, as many individuals continue abusing opioids or other drugs during agonist maintenance and drop out of treatment (Reece, 2009). As compared to methadone, treatment using buprenorphine is safer and more feasible, although effectiveness and limitations of both medications are generally comparable with treatment retention rates of 35-40% at 6 months (Hser et al., 2015).

The main alternative to agonist-based approach is treatment with the opioid antagonist naltrexone, which has been used in its oral form for the treatment of opioid dependence since 1984. The approval of long-acting (XR) injectable naltrexone (XR-NTX) in 2010 represents a substantial advance, circumventing the need for daily medication adherence, a major challenge with oral preparations. Naltrexone blocks the effects of opioids, while producing no agonist effects itself. Since naltrexone acts by a different mechanism it may be helpful to patients who are not suitable or interested in agonist maintenance, or have failed prior trials of agonist due to side effects or continuing use. However widespread implementation of naltrexone treatment has been limited by: 1) difficulties transitioning patients at the outset of treatment from opioid use onto naltrexone, and 2) persisting withdrawal-like symptoms that some patients experience which may contribute to the dropout prior to the second monthly injection.

Naltrexone can only be started after the completion of opioid withdrawal, which itself is uncomfortable and many patients relapse before achieving long-enough abstinence. Procedures for rapid transition to naltrexone by combining detoxification with oral naltrexone induction may decrease the wait time before the first injection but are labor intensive because of the need to frequently adjust adjunctive medications in response to precipitated withdrawal. As a result, the dropout rate in the first few days is high, and burden on staff is substantial, both factors limiting the clinical feasibility of this approach (Gowing et al., 2009). Decreasing the severity of withdrawal patients experience during the first days in treatment may allow more patients to receive the first injection.

We propose to test a new method of transitioning patients from opioid agonist onto antagonist that may have higher tolerability. It involves maintaining patients on a dose of BUP that will block craving and withdrawal while gradually increasing dose of naltrexone until a final blocking dose is reached. Slow increase of naltrexone will likely minimize the severity of withdrawal.

Some patients continue experiencing withdrawal-like symptoms during the first few weeks after receiving XR-NTX. The common strategy to manage them involves administering adjunctive medications such as clonazepam, clonidine, zolpidem trazodone etc. It has been observed that adding buprenorphine after the patient received a full blocking dose of naltrexone will not produce mu opioid agonist effect (as it is blocked

by naltrexone) but kappa antagonist effects of buprenorphine will remain which may decrease craving and residual withdrawal symptoms and therefore will help patients to stabilize on XR-NTX.

Improved strategies of naltrexone induction and stabilization will permit expansion of its use to populations that currently opt for psychosocial-only approaches or those who chose to terminate treatment with agonists.

Specific Aims and Hypotheses

Specific Aims and Hypotheses

The goal of this pilot study is to test three new outpatient procedures to facilitate transition onto a long-acting, injectable form of naltrexone 380 mg (XR-NTX) in opioid-dependent individuals who are actively using opioids and are seeking treatment with naltrexone.

We are proposing to enroll 30 opioid-dependence participants, 10 into each of three procedures, for an open-label study of relapse prevention. We will enroll the first 10 participants in Procedure 1, the next 10 in Procedure 2, and the last 10 in Procedure 3. Treatment will be delivered in an outpatient setting including a phase of outpatient opioid withdrawal, followed by XR-NTX injection and another XR-NTX injection 4 weeks later. In addition, patients will receive a psychosocial intervention that will include elements of motivational interviewing and cognitive-behavioral relapse prevention therapy.

The primary aim is to test the the feasibility, safety and efficacy of the new methods to improve tolerability of naltrexone induction and reducing attrition during detoxification and the first month of naltrexone treatment.

Primary Hypothesis 1: Adjunctive treatment with buprenorphine 4 mg during the first 5 weeks of naltrexone maintenance will improve opioid abstinence and treatment retention, defined as receiving the second XR-NTX injection.

Primary Hypothesis 2: Providing buprenorphine 4 mg daily during gradual 9-day titration of oral naltrexone will improve tolerability and success of XR-NTX induction, defined as receiving the first XR-NTX injection.

Primary Hypothesis 3: Providing buprenorphine 4 mg daily during gradual 9-day titration of oral naltrexone and adjunctive treatment with buprenorphine 4 mg during the first 5 weeks of naltrexone maintenance will significantly improve opioid abstinence and treatment retention, defined as receiving the second XR-NTX injection.

Primary Aim 4: To examine in biofluid-derived extracellular vesicle content for the existence of biomarkers related to naltrexone treatment.

Description of Subject Population

Sample #1

Specify subject population

Adults with current Opioid Use Disorder

Number of completers required to accomplish study aims

15

Projected number of subjects who will be enrolled to obtain required number of completers

30

Age range of subject population

18-60

Gender, Racial and Ethnic Breakdown

Both genders and all ethnic groups are eligible. It is estimated that the sample will be 60% male, 40% female, 50% Caucasian, 30% Hispanic-American, 15% African-American, and 5% other minorities based on data from previous trials.

Description of subject population

Prospective participants must be adult (18 to 60 years of age) and meet criteria for current opioid use disorder by history and urine toxicology. Other substance use diagnoses are not exclusionary since multiple substance abuse is common in this population, and such an exclusion would rule out a large proportion of the population and limit the generalizability of the study. However, physiological dependence on alcohol or sedative-hypnotics with impending withdrawal is exclusionary. Maintenance on methadone or other long-acting agonist (e.g. buprenorphine) or regular use of illicit methadone (> 30 mg per week) is exclusionary. Prospective participants cannot have concurrent psychiatric or medical conditions that would interfere with

participation (e.g. mania, psychosis, suicidality, pregnancy or failure to use adequate contraception).

Recruitment Procedures

Describe settings where recruitment will occur

All potential participants will be evaluated at the **BSU** clinic at the New York State Psychiatric Institute.

How and by whom will subjects be approached and/or recruited?

All patients will be seen by one of our psychiatrists or Master's level therapist for a screening evaluation and mental status examination as part of routine admission procedures or BSU clinic . Patients who appear to meet criteria are told about the study and offered further evaluation. Final informed consent for the study will be obtained after full psychiatric and medical workup is complete.

The physicians listed above work regular weekly shifts, know the protocol well, and are able to explain study consent to the participant. Procedures for training staff physicians in each protocol and consent form include initial presentations by the Principal Investigator at weekly staff meetings, and weekly discussion of inclusion/exclusion criteria and study eligibility for each screening participant.

How will the study be advertised/publicized?

Once approved by the IRB, advertisements for study will be placed in local newspapers and radio stations. Additionally, prospective participants are recruited by word of mouth and through liaison to other local clinical services.

Do you have ads/recruitment material requiring review at this time?

No

Does this study involve a clinical trial?

Yes

Please provide the NCT Registration Number

NCT03113409

Concurrent Research Studies

Will subjects in this study participate in or be recruited from other studies?

No

Inclusion/Exclusion Criteria

Name the subject group/sub sample

Adults with current Opioid Use Disorder ages 18-60

Create or insert table to describe the inclusion criteria and methods to ascertain them

1) Age 18-60. (Clinical interview)

-
- 2) Meets DSM-5 criteria for current opioid use disorder (moderate-severe) of at least six months duration, supported by urine toxicology OR COWS score $>$ or $=6$ OR Naloxone Challenge . (Clinical & MINI Interview; urine toxicology or COWS score $>$ or $= 6$ OR Naloxone Challenge (see Procedures))
- 3) Voluntarily seeking treatment for opioid dependence. (Clinical interview)
- 4) In otherwise good health based on complete medical history and physical examination (Clinical interview and physical examination; vital signs, ECG, laboratory tests (hematology, blood chemistry, urinalysis) within normal ranges (AST or ALT $<$ 3 times normal).)
- 5) Able to give written informed consent. (Clinical interview and mental status exam)
Create or insert table to describe the exclusion criteria and methods to ascertain them
- 1) Methadone maintenance treatment or regular use of illicit methadone ($>$ 30 mg per week). (Clinical interview; urine toxicology)
- 2) Maintenance on, or regular use of buprenorphine or other long-acting narcotic agonists. (Clinical interview; urine toxicology)
- 3) Pregnancy, lactation, or failure in a sexually active woman to use adequate contraceptive methods. (Clinical Interview, physical examination, urine pregnancy test during screening, serum pregnancy test at screening, and urine test on day of administration of XR-NTX)
- 4) Active medical illness which might make participation hazardous, such as untreated hypertension, acute hepatitis with AST or ALT $>$ 3 times normal, AIDS (CD4 count under 200 currently or medically ill with an opportunistic infection), unstable diabetes. (Clinical interview, physical examination, laboratory (Chem-20, CBC, urinalysis), ECG)
- 5) Active psychiatric disorder which might interfere with participation or make participation hazardous, including DSM-5 Schizophrenia or any psychotic disorder, severe Major Depressive Disorder, or suicide risk or 1 or more suicide attempts within the past year. (Clinical and MINI interview, clinical mental status examination, discussions with previous psychiatrist or treatment provider if formerly in treatment.)
- 6) Physiologically dependent on alcohol or sedative- hypnotics with impending withdrawal. Other substance use diagnoses are not exclusionary. (Clinical & MINI interview; urine toxicology)
- 7) History of allergic or adverse reaction to buprenorphine, naltrexone, naloxone, clonidine, or clonazepam. (Clinical interview)
- 8) Chronic organic mental disorder (e.g. AIDS (CD4 count under 200 currently or medically ill with an opportunistic infection) dementia). (Clinical interview, mental status, physical and laboratory examination)
- 9) History of accidental drug overdose in the last 3 years as defined as an episode of opioid-induced unconsciousness or incapacitation, whether or not medical treatment was sought or received. (Clinical interview)

10) Painful medical condition that requires ongoing opioid analgesia or anticipated surgery necessitating opioid medications. (Clinical interview, physical examination)

Waiver of Consent/Authorization

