### **Study Objectives and Endpoints**

The primary objective of this pilot open-label study is to evaluate three new outpatient pharmacological procedures to facilitate transition onto a long-acting, injectable form of naltrexone 380 mg (XR-NTX).

The primary aim is to test the feasibility, safety, and effectiveness of the new methods to improve tolerability of naltrexone induction and reducing attrition during detoxification and the first month of naltrexone treatment.

The primary endpoint is the receipt of the two injections of XR-naltrexone given first after completion of the detoxification and induction procedure and the second administered 4 weeks later.

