### **Study Participants and Design**

Participants in the study are individuals with opioid use disorder (OUD) who are actively using opioids and are seeking treatment with naltrexone as a relapse-prevention intervention

This is a non-randomized and unblinded trial.

Interested participants will be first screened to determine study inclusion and exclusion criteria. Eligible participants will receive treatment in an outpatient setting and will be consecutively enrolled into treatment with one of the three study procedures: Procedure 1, Procedure 2, and Procedure 3.

Treatment will include following phases: 1) opioid withdrawal management, 2) initiation of naltrexone given orally followed by an injection of XR-naltrexone, 3) Outpatient relapse-prevention treatment, 4) administration of the second XR-naltrexone injection approximately 4 weeks after the first injection.

In addition to pharmacological treatment, all participants will receive a psychosocial intervention that will include elements of motivational interviewing and cognitive-behavioral relapse prevention therapy.

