### **Sample Size**

Total enrollment goal is approximately 30 adult participants with OUD. We will enroll the first 10 participants in Procedure 1, the next 10 in Procedure 2, and the last 10 in Procedure 3.

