## **Study Hypotheses**

Primary Hypothesis Procedure 1: Adjunctive treatment with buprenorphine 4 mg during the first 5 weeks of naltrexone maintenance will improve opioid abstinence and treatment retention, defined as receiving the second XR- NTX injection.

Primary Hypothesis Procedure 2: Providing buprenorphine 4 mg daily during gradual 9-day titration of oral naltrexone will improve tolerability and success of XR-NTX induction, defined as receiving the first XR-NTX injection.

Primary Hypothesis Procedure 3: Providing buprenorphine 4 mg daily during gradual 9-day titration of oral naltrexone and adjunctive treatment with buprenorphine 4 mg during the first 5 weeks of naltrexone maintenance will improve opioid abstinence and treatment retention, defined as receiving the second XR-NTX injection.

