## **Study Analysis**

The primary analysis is a summary statistic of the percent of participants who initiate treatment and receive two consecutive XR-naltrexone injections (Procedures 1 and 3) or the percent of participants who complete detoxification and receive the first XR-naltrexone injection.

In addition, a percentage of patients that received the second injection among those that receive the first injection will also be calculated (Procedure 1 and 3). A summary of the adverse events and serious adverse events will also be presented

Baseline demographic characteristics will be summarized. For continuous variables, descriptive statistics (n, mean, SD, and range) will be provided. For categorical variables, patient counts, and percentages will be provided.

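### Primary Hypotheses 1–3 claim improvement without a stated reference rate, threshold or test, and the SAP's percentages leave out both-injection receipt for Procedure 2 and any abstinence or withdrawal summary

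*Protocol*

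**What the plan says.** **Hypotheses.** Protocol, Specific Aims and Hypotheses, gives one primary hypothesis per procedure. Hypotheses 1 and 3 concern abstinence and retention, with retention meaning the second injection. Hypothesis 2 concerns tolerability and receipt of the first injection. Hypothesis 3 reads "during the first 5 weeks of naltrexone maintenance will significantly improve opioid abstinence and treatment retention". The SAP (Study Hypotheses) has the same three without the word *significantly*; for Procedures 1 and 3 the phrase is "during the first 5 weeks of naltrexone maintenance will improve opioid abstinence and treatment retention".

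**Design.** SAP, Study Participants and Design: "This is a non-randomized and unblinded trial". SAP, Sample Size: "We will enroll the first 10 participants in Procedure 1, the next 10 in Procedure 2, and the last 10 in Procedure 3".

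**Endpoint.** SAP, Study Objectives and Endpoints: "The primary endpoint is the receipt of the two injections of XR-naltrexone", with no procedure excepted. The Protocol's Lay Summary likewise makes the percentage with a second injection the primary outcome of the study, and lists withdrawal and illicit opioid use as secondary outcomes. SAP, Study Outcome Measures, then gives Procedure 2 the first injection as its primary outcome and mentions residual withdrawal as an additional assessment.

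**Analysis.** SAP, Study Analysis, sets the main result for Procedures 1 and 3: "The primary analysis is a summary statistic of the percent of participants who initiate treatment and receive two consecutive XR-naltrexone injections". The other main figure, which by the SAP's outcome measures belongs to Procedure 2, is "the percent of participants who complete detoxification and receive the first XR-naltrexone injection". A conditional figure is planned as well, restricted to Procedures 1 and 3: "a percentage of patients that received the second injection among those that receive the first injection will also be calculated". The rest is an adverse event summary and baseline descriptives. No interval, threshold or test is mentioned.

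**The concern.** A hypothesis that something will improve needs an answer to the question: compared with what? If no reference rate is stated before the data are seen, any percentage can later be read as success or as failure. The word *significantly* in Protocol Hypothesis 3 also suggests a test that neither document contains.

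The second problem concerns reporting. If the SAP is followed as written, the endpoint that both documents set for the whole study will not be reported for one of the three procedures. Outcomes named in the primary hypotheses, or listed as secondary, will have no planned result, and their summaries would then be chosen after the data are known.

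**Working it through.** **1. The plan's own figure.** Enrolment is 3 × 10 = 30. No alpha, power, effect size or expected injection rate accompanies it, so there is no sample-size calculation to reproduce.

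**2. Search for a reference rate.** Three figures in the Protocol might seem to serve:

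| Figure | Where | Why it is not a reference |
|---|---|---|
| 35–40% retention at 6 months | Background, Significance and Rationale | Agonist treatment; different endpoint and time point |
| Earlier experience in 30 participants | Procedure 2, Rationale | No success rate given |
| 15 completers of 30 enrolled | Description of Subject Population | Recruitment figure, not tied to either injection |

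**3. Precision of the planned percentages.** The exact (Clopper–Pearson) 95% limits for x of n are: lower = 2.5% quantile of Beta(x, n − x + 1); upper = 97.5% quantile of Beta(x + 1, n − x). For x = n the upper limit is 1 and the lower is 0.025^(1/n); at n = 10 this is 0.025^0.1 = 0.692. The counts below are illustrative, because the documents give no expected rate for either injection.

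| Count | Percentage | Exact 95% interval |
|---|---|---|
| 5/10 | 50% | 19–81% |
| 7/10 | 70% | 35–93% |
| 8/10 | 80% | 44–97% |
| 10/10 | 100% | 69–100% |
| 5/7 (second given first) | 71% | 29–96% |

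So 8/10 does not exclude a true rate of 45%, and 10/10 does not exclude 70%.

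**4. Would a reference rate make the claim testable?** Yes, though weakly. Take the smallest r for which P(X ≥ r) ≤ 0.05 when X is Binomial(10, p0). The reference rates p0 are assumptions:

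| Assumed p0 | Success rule | One-sided alpha | Power at an assumed true rate |
|---|---|---|---|
| 30% | ≥ 6/10 | 0.047 | 63% at 60% |
| 40% | ≥ 8/10 | 0.012 | 38% at 70% |
| 50% | ≥ 9/10 | 0.011 | 38% at 80% |

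**5. Could the procedures serve as comparators for each other?** They enrol one after another, so any contrast is confounded with enrolment order. It would also have little power: for 10 against 10, a two-sided Fisher test at 0.05 has about 5.5% power for assumed rates of 50% and 70%, 13% for 50% and 80%, and 30% for 50% and 90%.

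**6. Stated outcomes against planned outputs.**

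| Outcome | Where stated | Output in SAP, Study Analysis |
|---|---|---|
| Both injections, Procedures 1 and 3 | Both documents | Percentage, no interval |
| First injection, Procedure 2 | Hypothesis 2; SAP, Study Outcome Measures | Percentage, no interval |
| Second or both injections, Procedure 2 | Study-level endpoint in both documents | None |
| Abstinence or illicit opioid use | Hypotheses 1 and 3; Lay Summary | None |
| Withdrawal | Lay Summary; SAP, Study Outcome Measures | None |

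Procedure 2 participants are scheduled for a second injection four weeks after the first (Protocol, Procedure 2), so the missing percentage can be calculated. It concerns 10/30, one third of the sample.

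**7. Which abstinence data fit the hypotheses?** Hypotheses 1 and 3 refer to weeks 1–5 after the first injection. The End-of-Study Form records abstinence over the last four weeks in the trial, and the final study day is 28 days after the second injection. With injections four weeks apart, a completer's form covers roughly weeks 5–8, which overlaps the hypothesis period only in week 5. Serial urine toxicology, at twice-weekly visits in weeks 1–8, covers the whole period.

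**The case against.** The strongest reply is that this is an open-label pilot, that both documents say so, and that the SAP makes no inferential claim and has already dropped *significantly*. A descriptive analysis of 10 people per procedure is acceptable, the cohort size is disclosed, and a reader can derive an interval from x/10. All of this stands, and no control arm, test or larger sample is asked for. It does not remove the mismatch with hypotheses of improvement, which the SAP keeps, and it does not excuse outputs that even a descriptive plan should contain.

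Nor is the background silent on a comparator. It describes high dropout during rapid induction, loss before the second injection and the usual adjunctive medications. Procedure 1 is presented as replicating a published method, and Procedure 3 as a combination of procedures. A qualitative comparison is therefore implied; what is missing is a stated comparator with a rate.

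The first injection is also used consistently as the outcome of Hypothesis 2. The conflict is with the study-level endpoint, and reporting both resolves it.

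A reader might infer that cohorts of 10 rule out any finding of improvement. The single-arm rules above show otherwise: the main obstacle is the absent reference rate, and the small cohorts then limit power. A reader might also take 15 completers of 30 as an expected success rate. The Protocol does not link that figure to an injection, so it is not used here.

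**Conclusion.** The point holds, and the plan should be amended. As written, no result can confirm or refute Primary Hypotheses 1–3, because the documents state no reference rate, threshold or test. The planned percentages are legitimate estimates, but at 10 per procedure they are imprecise, with exact intervals running from 19–81% at 5/10 to 69–100% at 10/10. Separately, the SAP omits the study-level primary endpoint for one third of the sample and plans no summary of abstinence or withdrawal.

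The omissions and the missing reference can be seen in the text and rest on no numerical assumption. The intervals depend only on n = 10 and on illustrative counts; the success rules and power figures also depend on assumed rates. The documents do not support a conclusion that the pilot design is unsound, that the SAP plans a significance claim, or that participant safety is affected.

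**What to change.** 1. **SAP, Study Outcome Measures and Study Analysis.** Report receipt of the first injection, and of both injections, for all three procedures, and extend the second-given-first percentage to Procedure 2. State that the unconditional percentages use all participants enrolled in that procedure as the denominator; the separate conditional percentage already implies this. Give an exact 95% interval with every percentage. State that the first injection is the outcome of the Procedure 2 hypothesis and that both injections are the study-level endpoint.

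2. **Hypotheses 1–3, both documents.** Reword them as estimation objectives and delete *significantly* from Protocol Hypothesis 3. If the sponsor wants to keep a claim of improvement, the alternative is to pre-state, for each procedure, a justified reference rate and an exact single-arm success rule.

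3. **Abstinence and withdrawal.** Add a descriptive summary by procedure of opioid use from serial urine toxicology over the period named in the hypotheses, and of COWS and SOWS scores. Report the End-of-Study abstinence status only as a separate late-period measure.

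4. **Contrasts.** None need be added. Label any that is reported as descriptive and confounded with enrolment order.

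The cost is wording in both documents and some extra descriptive figures from data already collected. Participants, treatment and assessments do not change. The downside is a weaker stated claim and a slightly longer results table.
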